The Kenward-Roger approximation will be used to estimate denominator degrees of freedom and adjust standard errors. The point estimates of the adjusted mean difference between treatment arms at each visit, together with the corresponding two-sided 95% confidence intervals and p-values will be presented. The primary treatment comparison will be the contrast between treatments at Week 26.

Procedures to follow if the MMRM analysis fails to converge will be described in the Trial Statistical Analysis Plan.

To assess the robustness of the primary analysis result, sensitivity analyses of the primary endpoint are planned in which the same strategy for handling intercurrent events as used for the primary analysis will be applied.

Page 81 of 112

Proprietary confidential information © 2023 Boehringer Ingelheim International GmbH or one or more of its affiliated companies

- For patients who had early treatment termination due to exacerbation or acute episode or an event considered to be drug-related, missing data after the intercurrent event will be imputed through a reference-based multiple imputation method, i.e., using the observed off-treatment data from patients in the same treatment arm to impute the missing off-treatment data. All other missing data, e.g. missing on-treatment data or missing data after other intercurrent events, will be imputed using the observed on-treatment data from all randomized patients in the same treatment arm.
- For all missing data, a reference-based approach using observed off-treatment data from the same treatment arm to impute missing data will be applied for multiple imputation. This would be a conservative approach to missing data assuming missing not at random.
- For all missing data, apply a jump-to-reference (J2R) method for multiple imputation, i.e. assume patients in BI arm switch to the placebo arm distribution following the missingness. This would be a conservative approach to missing data assuming missing not at random.

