After applying the above different multiple imputation methods for the missing data (including the "set-to-missing" data), an Analysis of Covariance (ANCOVA) model including the fixed effects of treatment, categorical effect of stratification factor using screening MCCB overall composite T-score, and baseline MCCB overall composite T-score will be fitted for the primary endpoint at Week 26. Rubin's rules will be applied to derive the single point estimates and the corresponding standard errors from the multiple imputations (R12-2094).

In addition, as a supplement to the strategy for handling the intercurrent events as used in the primary analysis and sensitivity analyses, we will conduct the following supplementary analyses for the primary endpoint:

- Handle all intercurrent events using treatment policy approach and then apply the same MMRM model as used in the primary analysis assuming missing at random.
- Handle all intercurrent events using hypothetical approach, i.e. censoring all data after the intercurrent event, and apply the MMRM model as used in the primary analysis assuming missing at random.
- Consider different strategies for handling intercurrent events, e.g. consider different set of intercurrent events to be handled using treatment policy, consider using while on treatment strategies.

More details on the sensitivity analyses and the supplementary analyses will be provided in the TSAP.

To address the COVID-19 pandemic or other potential public health crisis, BI plans to investigate logistical mitigation measures introduced for COVID-19 and develop statistical assessments accordingly, e.g. if the option for remote visits is introduced, BI will compare remote to in-person visits.

In addition, BI will summarize the prevalence of intercurrent events caused by COVID-19, e.g., COVID-19 infection as an AE; discontinuation of study treatment because of "administrative" reasons such as lack of availability of medical procedures and treatment, quarantine, travel restrictions, etc. The resulting intercurrent events lead to missing outcomes. Some patients may still be able to continue treatment if they have sufficient drug

c33087946-03

Page 82 of 112 Proprietary confidential information © 2023 Boehringer Ingelheim International GmbH or one or more of its affiliated companies

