7.4 RANDOMISATION

Eligible patients will be randomised in equal ratio to Iclepertin 10mg arm and the placebo arm. The randomisation will be implemented in blocks to achieve balanced allocation to each treatment arm. In addition, randomisation will be stratified by the screening MCCB overall composite T-score (two strata: $<30, \ge 30$) with the cut-off values based on the characteristics of the MCCB overall composite T-score from historical data (R19-3841).

Page 86 of 112

Proprietary confidential information © 2023 Boehringer Ingelheim International GmbH or one or more of its affiliated companies

The randomization will be conducted via IRT. BI will arrange for the randomization and the packaging and labelling of trial medication. The randomization list will be generated using a validated system, which involves a pseudorandom number generator so that the resulting treatment will be both reproducible and nonpredictable. The block size will be documented in the CTR. Access to the codes will be controlled and documented.

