7.5 DETERMINATION OF SAMPLE SIZE

Results from a phase II proof of clinical concept and dose ranging trial (1346-0009, c31477880) show the largest mean improvement of Iclepertin vs. placebo in change from baseline to Week 12 in MCCB overall composite T-score is 2 points with the estimated standard deviation of approximately 5.8 at Week 12 (the estimated standardized effect size is about 0.35), and the largest mean improvement of Iclepertin vs. placebo in change from baseline to Week 12 in SCoRS interviewer total score is 1 point with the estimated standard deviation of approximately 5.5 at Week 12 (the estimated standardized effect size is about 0.2). For this phase III trial with a treatment duration of 26 weeks and considering a treatment effect under the proposed primary estimand framework (i.e. definition of intercurrent events and the corresponding handling strategies), we assume a standardized effect size of 0.35 in the sample size calculation for the primary and the two key secondary efficacy endpoints and also assess the power of the proposed sample size under different assumptions of the standardized effect sizes for the key secondary efficacy endpoints.

The method of the two-sample t-test with equal variances and equal n's using the software nQuery + nTerim 4.0 was used to calculate the sample size based on each of the primary and the key secondary efficacy endpoints individually. An effective sample size of 220 patients per arm, 440 patients in total, will detect a standardized effect size of 0.35 in the primary efficacy endpoint, or in any of the two key secondary efficacy endpoints individually, with 95% power under one-sided type I error rate of 0.025. With 220 patients per arm and one-sided type I error rate of 0.025, a standardized effect size of 0.31, 0.286, 0.268, and 0.25 can be detected for each of the primary and the two key secondary efficacy endpoints individually with 90%, 85%, 80%, and 75% power respectively.

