Proprietary confidential information © 2023 Boehringer Ingelheim International GmbH or one or more of its affiliated companies

Table 7.5: 1 Probability of success for each endpoint under different scenarios of effect sizes from simulations (con't)

-			T	1	1	,
Scenario #2 (assumed standardized effect sizes)	0.35	0.1	0.35	0.2	0.275	
Probability of rejecting null from 1000000 simulations	95.6%	12.8%	88.6%	37.5%	60.9%	88.9%
Scenario #3 (assumed standardized effect sizes)	0.35	0.1	0.3	0.2	0.2	
Probability of rejecting null from 1000000 simulations	95.6%	12.6%	78.6%	32.4%	32.4%	79.6%
Scenario #4 (assumed standardized effect sizes)	0.35	0.1	0.25	0.2	0.275	
Probability of rejecting null from 1000000 simulations	95.6%	12.5%	62.7%	30.0%	46.7%	65.2%
Scenario #5 (assumed standardized effect sizes)	0.35	0	0	0.2	0.275	
Probability of rejecting null from 1000000 simulations	95.6%	1.3%	1.3%	1.5%	2.0%	2.4%

With 220 evaluable patients per arm, one-sided family-wise type I error=0.025, correlation between the endpoints is 0.2, truncation parameter $\gamma = 0.2$, and the gatekeeping procedure as shown in Figure 7.1: 1.

Based on the proportions of early treatment termination, patients with missing data and missing data patterns as observed in our phase II trial 1346-0009 and anticipating higher proportions of early treatment termination based on previous literatures in long-term antipsychotic trials and more patients with missing data in our phase III trial due to longer

Page 89 of 112

Proprietary confidential information © 2023 Boehringer Ingelheim International GmbH or one or more of its affiliated companies

treatment duration, we project 30% to 40% patients will prematurely terminate treatment in our phase III trial. Since BI will take every measure to collect all data at the planned visits from early dropout patients, we anticipate 25% to 50% of these early dropouts will have efficacy outcomes collected after treatment termination and can be used in the analysis. Based on these estimations, we will apply 25% correction for missing data in the sample size calculation for this phase III trial. This gives a total number of 586 randomized patients for the phase III trial, with 293 randomized patients in each treatment arm.

c33087946-03

Clinical Trial Protocol

Page 90 of 112

Proprietary confidential information © 2023 Boehringer Ingelheim International GmbH or one or more of its affiliated companies

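### As worded in the protocol, the all-treatment-policy supplementary analysis uses a MAR MMRM with no on/off-treatment term, so it would lean towards the on-drug effect if benefit fades after stopping

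*Protocol*

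**What the plan says.** Protocol 7.2.2 lists supplementary analyses for change in MCCB overall composite T-score at Week 26. The first reads: "Handle all intercurrent events using treatment policy approach and then apply the same MMRM model as used in the primary analysis", with missing data taken as missing at random. The primary model is written out in the same section and again, with code, in SAP 7.4.1 and 10.2.1. It has treatment by visit, screening stratum and baseline by visit, with an unstructured covariance over visits. No term separates on-treatment from off-treatment scores.

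The sensitivity analyses in Protocol 7.2.2 do make that separation. For stops due to exacerbation or a drug-related event, the first one works by "using the observed off-treatment data from patients in the same treatment arm to impute the missing off-treatment data". Two more cover all missing data: one imputes from same-arm off-treatment scores, the other is jump-to-reference. All three keep the mixed intercurrent-event strategy of the primary estimand.

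On the amount of missing data, Protocol 7.5 states "we project 30% to 40% patients will prematurely terminate treatment in" this trial, and "we anticipate 25% to 50% of these early dropouts will have efficacy outcomes collected after treatment termination".

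Protocol 7.2.3 carries similar sensitivity and supplementary analyses to SCoRS and VRFCAT. Protocol 7.2.2 leaves further detail to the SAP.

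**The concern.** A treatment-policy estimate needs the Week 26 outcome of stoppers as it is after stopping. Where that outcome is missing, this MMRM predicts it from the patient's baseline, stratum and any Week 12 score, together with the arm's Week 26 mean. Most of the scores behind that mean come from patients still on drug. If the drug-placebo difference shrinks after stopping, the prediction is too favourable, and the estimate lands between the treatment-policy effect and the on-drug effect.

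This is the analysis a reader will consult to learn what happens regardless of stopping. If it sits close to the on-drug effect by construction, agreement with the primary result reassures less than it appears to. The same holds for its SCoRS and VRFCAT versions.

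**Working it through.** **Inputs from Protocol 7.5**

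- Effect D = 2 points and SD 5.8, from phase II at Week 12: "in MCCB overall composite T-score is 2 points with the estimated standard deviation of approximately 5.8 at Week 12".
- Share stopping early, s = 30–40%.
- Share of stoppers with later outcomes, r = 25–50%, so 50–75% have none.
- 293 randomized per arm.

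**Assumptions not in the documents**

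- The 2-point effect also holds at Week 26.
- Stopping is equal in both arms.
- A fraction f of the effect is kept off drug. The documents give no value, so f = 0, 0.5 and 1 are shown.

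**Step 1: the plan's own figures.** The protocol states: "An effective sample size of 220 patients per arm, 440 patients in total, will detect a standardized effect size of 0.35" "with 95% power under one-sided type I error rate of 0.025". A two-sample noncentral t calculation at 220 per arm gives 95.6%, equal to Table 7.5:1. The 25% correction gives 440/0.75 = 586.7, against 586 stated. The planning inputs reproduce.

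**Step 2: how much is filled in, and from whom.**

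- Share of all patients who stop with no later score: s(1−r), from 0.30×0.50 = 15% to 0.40×0.75 = 30%.
- Share of observed Week 26 scores that are on drug: (1−s)/[(1−s)+s·r], from 0.60/0.80 = 75% to 0.70/0.775 = 90%.

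**Step 3: target and estimate.**

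- Treatment-policy target = D[(1−s)+s·f].
- MAR MMRM without an off-treatment term ≈ D[(1−s)+s·r·f]/[(1−s)+s·r].

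Example with s = 35%, r = 37.5%, f = 0: target 2×0.65 = 1.30; estimate 1.30/(0.65+0.131) = 1.66.

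| s, r | Target, f=0 | MMRM, f=0 | Excess | Target, f=0.5 | MMRM, f=0.5 | Excess |
|---|---|---|---|---|---|---|
| 30%, 50% | 1.40 | 1.65 | 0.25 (18%) | 1.70 | 1.82 | 0.12 (7%) |
| 35%, 37.5% | 1.30 | 1.66 | 0.36 (28%) | 1.65 | 1.83 | 0.18 (11%) |
| 40%, 25% | 1.20 | 1.71 | 0.51 (43%) | 1.60 | 1.86 | 0.26 (16%) |

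At f = 1 both equal 2 and the excess is zero.

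**Step 4: check by simulation.** A two-visit maximum-likelihood fit was run with 1,000,000 per arm, Week 12 seen for all, and Week 12/26 correlation 0.5 or 0.8.

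- All stoppers still on drug at Week 12, f = 0: 1.64–1.65, 1.66 and 1.71–1.72 for the three rows, matching the formula.
- Half of stoppers already off drug at Week 12, f = 0: 1.55–1.59, 1.51–1.58 and 1.51–1.58, an excess of 11–32%.

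A smaller fit (20,000 per arm, 6 repeats, correlation 0.7) gave 1.62 against 1.40 at its lowest, which is 16%. Taken together, the full-loss range is about 16–43%.

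**Step 5: donors for an off-treatment imputation.** 293×0.30×0.25 = 22 to 293×0.40×0.50 = 59 per arm.

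**The case against.** **The SAP may already deal with it.** The public SAP goes from 7.4.1 to 7.5, although 7.5.2 cites a 7.4.3, and from 10.2 to 10.7. The parts that would specify this analysis are not visible. What is visible points towards the issue: Section 6.3 uses on/off-treatment status in models and imputations, and references 8 and 10 concern, by title, a compliance variable under incomplete follow-up and estimation for the treatment policy strategy. This stands. A reader might infer that the final plan has no off-treatment term, but the documents support that only for the protocol. Against this, the visible list of changes in SAP Section 4 mentions no change to this estimator, so if the method was replaced, the two documents need aligning.

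**Close substitutes are planned.** If no effect survives stopping, jump-to-reference gives about D(1−s) = 1.2–1.4, the target itself. Imputing all missing data from off-treatment scores is near the fix below. This stands as mitigation: the trial does not lack a conservative check. But both analyses sit under the primary strategy, which discards observed scores after hypothetical-strategy stops, so neither repairs this estimand.

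**The direction is not established.** A reader might infer that the effect is overstated outright. No document gives an off-drug effect. The protocol calls off-treatment imputation conservative and sets a 12-day residual effect period. Both are consistent with fading benefit, but neither is evidence of its size.

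**Not every stopper without a later score is model-filled.** SAP Table 6.7:1 maps any MCCB from day 127 to Week 26, and an early end-of-treatment visit is due within 7 days of the last dose. With evenly spread stops, about 57/182 = 31% fall in that window. Such a score lies inside the residual period and counts as on drug, so it pushes the same way, but through visit mapping. Under the same table, an earlier stopper's end-of-treatment score can stand as Week 12. That makes the 11–32% case a favourable one for patients who leave no later score.

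**Holding the estimator fixed has a purpose.** It isolates the effect of changing the intercurrent-event strategy. This is a good reason to keep the MMRM as a display.

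**Conclusion.** The point holds for the protocol as written: the stated estimator does not match its own estimand when half or more of the stoppers leave no later outcome. With a 2-point on-drug effect and equal stopping in both arms, the estimate would exceed the treatment-policy effect by about 16–43% if all benefit is lost on stopping, 11–32% if half of stoppers are already off drug at an observed Week 12, 7–16% if half the benefit persists, and not at all if all of it persists.

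A reader might infer that the trial's main result is at risk. It is not. This analysis is supplementary and outside the gatekeeping procedure of Protocol 7.1, so the primary estimate, power and type I error do not depend on it. It is an inexpensive improvement to a robustness analysis.

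**What to change.** For the all-treatment-policy supplementary estimand, and its SCoRS and VRFCAT versions:

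- Keep all observed off-treatment scores.
- Impute scores missing after permanent discontinuation from observed off-treatment data in the same arm.
- Impute missing on-treatment scores from on-treatment data in the same arm.
- Apply the ANCOVA and Rubin's rules already specified in Protocol 7.2.2.
- Show the MAR MMRM as a secondary display, and leave the primary analysis as it is.

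If the full SAP already does this, or carries an equivalent on/off-treatment term, only the protocol wording needs aligning with it.

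The cost is some text and one more run of an imputation already planned. The supplementary confidence interval will be wider, by an amount not calculated here. With about 22–59 off-treatment donors per arm, the imputation could be unstable at the low end. The fix leaves untouched any early end-of-treatment score that the visit windows map to Week 26.

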7.2.3 Secondary endpoint analyses

For the two key secondary efficacy endpoints of change from baseline to Week 26 in SCoRS interviewer total score and adjusted total time T-score in VRFCAT, as well as the secondary efficacy endpoint of change from screening to Week 24 in PRECIS total score, the same strategy for handling the intercurrent events in the primary estimand analysis and a similar MMRM analysis used for the primary efficacy endpoint will be conducted to obtain the adjusted mean treatment effect between BI and placebo in terms of change from baseline to Week 26 (from screening to Week 24 for PRECIS total score). This MMRM model includes the discrete fixed effects of treatment at each visit, fixed categorical covariate of the stratification factor using the screening MCCB overall composite T-score, and continuous fixed effects for the corresponding baseline endpoint value at each visit. Visit will be treated as the repeated measure with an unstructured covariance structure to model the within-subject measurements. Subjects will be considered as a random effect. The primary treatment comparison is the contrast between treatments at Week 26 (Week 24 for PRECIS total score). For change from baseline to Week 26 in the T-score of the number of correct responses on ToL, an analysis of covariance (ANCOVA) model including treatment, stratification factor of screening MCCB overall composite T-score ($<30, \ge 30$), and baseline number of correct responses on ToL T-score will be fitted to the data.

Similar sensitivity and supplementary analyses as planned for the primary efficacy endpoint will also be conducted for the two key secondary efficacy endpoints.

Page 83 of 112

Proprietary confidential information © 2023 Boehringer Ingelheim International GmbH or one or more of its affiliated companies

7.2.5 Safety analyses

AEs will be coded using the Medical Dictionary for Drug Regulatory Activities (MedDRA). Standard BI summary tables and listings will be produced.

All treated patients will be included in the safety analysis and will be summarized under the actual trial medication received at randomization. In general, safety analyses will be descriptive in nature and will be based on BI standards. No hypothesis testing is planned.

Statistical analysis and reporting of AEs will concentrate on treatment-emergent AEs. To this end, all AEs occurring between the start of treatment and the end of the REP will be considered 'treatment-emergent'. The REP is defined as 12 days after the last dose of trial medication. AEs that start before first drug intake and deteriorate under treatment will also be considered as 'treatment-emergent'.

Frequency, severity, and causal relationship of AEs will be tabulated by system organ class and preferred term after coding according to the current version of the MedDRA.

Frequency tables for all AEs, protocol-specified AESI, SAE, AE leading to death, AE leading to discontinuation, investigator assessed drug-related AE and serious related AE will be generated for treatment-emergent AEs. In addition, summary statistics and descriptive analyses will be conducted for other safety parameters that are assessed using dedicated scales, including suicidality as assessed by C-SSRS, disease severity as assessed by total score and changes over time on AIMS, SAS and BARS scales for EPS and related movement impairments.

Laboratory data will be analysed both quantitatively as well as qualitatively. The latter will be done via comparison of laboratory data to their reference ranges. Values outside the reference range as well as values defined as clinically relevant will be highlighted in the listings. Treatment groups will be compared descriptively with regard to distribution parameters as well as with regard to frequency and percentage of patients with abnormal values or clinically relevant abnormal values.

Vital signs, physical examinations, or other safety-relevant data observed at screening, baseline, during the course of the trial and at the end-of-trial evaluation will be assessed with regard to possible changes compared to findings before start of treatment.

Withdrawal-related safety analysis

In addition to the main safety analysis, withdrawal-related safety analysis will be conducted separately and descriptive for AEs emerging during the off-treatment safety follow-up period. New AEs emerging during this 4-week safety period, compared to while the patient is still on-treatment, will be identified and assessed by contrasting the following analysing treatment periods:

- 4-week withdrawal period for AEs occurring from 1 day after last dose to 28 after last dose of trial medication, and
- Strictly on-treatment period for AEs occurring from the start of treatment to the last dose of trial medication.

Page 84 of 112

Proprietary confidential information © 2023 Boehringer Ingelheim International GmbH or one or more of its affiliated companies

This withdrawal-related safety analysis will also assess vital signs descriptively.

Change in withdrawal symptoms based on PWC-20 will be analysed descriptively.

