- ¹⁴ For patients not rolling over to the extension study: after the individual patient's end of the study, the investigator should report only any cancers of new histology and exacerbations of existing cancer, trial treatment related SAEs and trial treatment related AESIs of which the investigator may become aware of and only via the BI SAE form, please see section 5.2.6.2.1.
- ¹⁵ Duration of visits indicated in this Flow Chart are approximate estimates, actual time may vary as per site and patient requirements.
- ¹⁶ Visit 11 will be performed only by patients who prematurely discontinue trial drug but agree to continue trial participation. For patients who have permanently discontinued study medication the following procedures are no longer required: Dispense and administer IMP, IMP compliance check, AiCure review, PK Sampling, bio banking sampling.
- ¹⁷ If the patient permanently discontinues treatment early, the eEOT visit must be performed within 7 days of study drug discontinuation. The patient should be followed up according to guidance provided in section 6.2.3.4. For patients who permanently discontinue study medication the following procedures do not need to be performed: Dispense and administer IMP, IMP compliance check, AiCure review, PK Sampling, bio banking sampling and Physician Withdrawal Checklist at visit 10. For follow up of patients with Hb related issues, please refer to section 5.2.6.4
- 18 Safety follow-up visits must be completed after the EOT or early EOT visit. Each follow-up visit is to be scheduled from the EOT or early EOT visit (e.g. follow-up visit 1 should be conducted 7 days \pm 1 day from the EOT or early EOT visit).
- ¹⁹ Patients who finish the 26 weeks of treatment period in this study and the 4 weeks of safety follow-up, can rollover to the extension trial after completing follow-up visit 6.
- ²⁰ Study partner must complete the SCoRS and interviews at least at Visit 2 and EOT (please refer to inclusion criterion # 8)
- ²¹ Additional collection of the C-SSRS at an unscheduled visit may be done based on the investigator's discretion.
- X^H Haematology panel A and B only.

Page 8 of 112

Page 9 of 112

Proprietary confidential information © 2023 Boehringer Ingelheim International GmbH or one or more of its affiliated companies

TA	RI	\mathbf{F}	OF	CO	N	$\Gamma \Gamma N$	JTC
-1	DL	ינונ	v	,		יוניו	

TITLE I	PAGE	1
CLINIC	AL TRIAL PROTOCOL SYNOPSIS	2
FLOW (CHART	6
TABLE	OF CONTENTS	9
ABBRE	VIATIONS	13

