4.1.4 Drug assignment and administration of doses for each patient

Dispensing of medication kits for the double-blind treatment period will begin at Visit 2. Throughout the treatment period, 2 trial medication kits will be provided at each visit. Medication assignment will be provided through IRT. The assigned medication kit numbers must be entered in the eCRF, and the corresponding medication kits must be given to the patient. The duration of treatment is 26 weeks. At each of the visits, patients will receive supplies for a total of 4 weeks.

The first dose of study medication will be taken at the end of Visit 2 under supervision of the investigator or delegated site staff, after all Visit 2 assessments have been completed. In case the Visit 2 is split into 2 sequential days, the first dose of study medication should be taken on the second day of the split visit, after all Visit 2 assessments have been completed.

Throughout the study, patients should be instructed to take 1 tablet orally with water and with or without food after waking up. If a dose is missed by more than 12 hours, that dose should be skipped and the next dose should be taken as scheduled.

Patients should be instructed **not** to take their study medication at home on the day of the clinic visit as patients will be dosed at the site. Dosing should occur approximately 24 hours after the drug administration from the preceding day.

Page 44 of 112

Proprietary confidential information © 2023 Boehringer Ingelheim International GmbH or one or more of its affiliated companies

The last dose of study medication should be taken on the day before the EoT Visit. In case the EoT Visit is split into 2 sequential days, the last dose of study medication should be taken on the day before the first day of the split visit.

On longer visit days the dosing may occur in the afternoon.

A dose reduction of Iclepertin is not possible.

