#### 6. GENERAL ANALYSIS DEFINITIONS

## 6.1 TREATMENT(S)

For basic study information on treatments to be administered, assignment of treatment groups, select of doses, see CTP Section 4.

Table 6.1: 1 lists the two treatment groups in this study. Table 6.1: 2 defines the analysing treatment period for safety analyses. For this study, the residual effect period (REP) is defined as 12 days after the last dose of trial medication.

Table 6.1: 1 Treatment descriptions

Long Name	Short Name	
Placebo	Placebo	
Iclepertin 10 mg QD	Iclepertin 10 mg	

Table 6.1: 2 Analysing treatment periods (same for all treatment groups)

Analysing Treatment Period	Start Date	End Date
Screening period	Date of informed consent	Date of the first treatment administration – 1 day
On-treatment period	Date of the first treatment administration	Date of the last treatment administration + REP
Post-treatment period	Date of the last treatment administration + REP + 1 day	Date of the last per protocol visit
Strictly on-treatment period	Date of the first treatment administration	Date of the last treatment administration
4-week withdrawal period	Date of last treatment administration + 1 day	Date of last treatment administration + 28 day

REP is the residual effect period which is defined as 12 days after the last dose of trial treatment.

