#### 7.8.1 Adverse events

Unless otherwise specified, the analyses of AEs will be descriptive in nature. All analyses of AEs will be based on the number of subjects with AEs and not on the number of AEs. The reporting and analyses of AEs will follow the BI guideline (3). AEs will be coded with the most current version of MedDRA®.

For further details on summarization of AE data, please refer to (1, 3).

The analysis of AEs will be based on the concept of treatment emergent AEs. That means that all AEs occurring between the date of the first administration of trial treatment till the date of the last administration of trial treatment + residual effect period will be assigned to the ontreatment period. All AEs occurring before the first administration of trial treatment will be assigned to 'screening' and all AEs occurring after the residual effect period will be assigned to 'follow-up'. For details on the treatment definition, see Section 6.1.

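### The withdrawal AE analysis contrasts patient counts from 28 days with counts from up to 182 days without a stated exposure adjustment, so a moderate rise in AE types already seen on treatment can read as a fall

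*Protocol*

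**What the plan says.** Protocol 7.2.5 adds a separate, descriptive withdrawal-related analysis to the main safety analysis: "New AEs emerging during this 4-week safety period, compared to while the patient is still on-treatment, will be identified and assessed by contrasting" two analysis periods. These are:

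- "4-week withdrawal period for AEs occurring from 1 day after last dose to 28 after last dose of trial medication"
- "Strictly on-treatment period for AEs occurring from the start of treatment to the last dose of trial medication"

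SAP Table 6.1: 2 carries over both periods for both arms; the withdrawal period ends at "Date of last treatment administration + 28 day". On the unit of analysis, SAP 7.8.1 states: "All analyses of AEs will be based on the number of subjects with AEs and not on the number of AEs". On treatment length, Protocol 4.1.4 states: "The duration of treatment is 26 weeks".

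The visible list of AE tables at the end of SAP 7.8.1 has no table for the withdrawal period. SAP 7.9 visibly covers only the PWC-20. Neither document names a patient-time denominator or an equal-length comparator for this contrast.

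**The concern.** A longer period gives each patient more opportunity to have at least one event. A percentage of patients over up to 26 weeks is therefore not comparable with a percentage over 4 weeks. If the rate of an AE rises after stopping, but by less than the ratio of the period lengths, the two percentages side by side suggest that the AE became less frequent.

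The AE types most exposed are those already common on drug. Protocol 1.2 names headache, dizziness, somnolence, nausea and vomiting.

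The protocol's risk table (1.4.2) says that AEs after stopping have not been formally investigated and offers the 4-week follow-up as mitigation. Protocol 6.2.4 requires all follow-up visits so that the effects of stopping can be evaluated. The other planned AE tables do not isolate the early off-drug days: SAP 7.8.1 assigns AEs up to 12 days after the last dose to the on-treatment period, so its follow-up table starts at Day 13. In the visible text, this contrast is the only AE analysis that separates the first 12 days off drug.

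**Working it through.** **Period lengths, reproducing the plan's figures.** The flow chart puts EOT at Day 183, and Protocol 4.1.4 places the last dose on the day before, Day 182.

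- On-treatment period: Days 1 to 182 = 182 days = 26.0 weeks.
- Withdrawal period: last dose +1 to +28 = 28 days = 4.0 weeks.
- Ratio in a completer: 182/28 = 6.5.

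**Effect on patient percentages.** Assume a constant hazard within each period. Let p be the proportion of patients with the AE over 182 days and RR the true rate ratio, off versus on treatment, within an arm. The proportion over 28 days is then

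1 − (1 − p)^(28 × RR/182).

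For p = 10%:

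- RR = 1: 1 − 0.9^(28/182) = 1.6%
- RR = 3: 1 − 0.9^(84/182) = 4.7%
- RR = 6.5: 1 − 0.9^(182/182) = 10.0%, the break-even

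| On treatment (182 days) | RR 1 | RR 2 | RR 3 | RR 5 | RR 6.5 | RR 8 |
|---|---|---|---|---|---|---|
| 5% | 0.8% | 1.6% | 2.3% | 3.9% | 5.0% | 6.1% |
| 10% | 1.6% | 3.2% | 4.7% | 7.8% | 10.0% | 12.2% |
| 20% | 3.4% | 6.6% | 9.8% | 15.8% | 20.0% | 24.0% |

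The break-even is 6.5 whatever the incidence. With 293 patients per arm, all taken as completers for illustration, 10% with a tripled rate is about 29.3 patients on treatment against 13.9 off treatment.

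**The same case per patient-time.** The on-treatment rate is 100 × (−ln 0.9)/26 = 0.41 per 100 patient-weeks. Tripled, it is 1.22. On this scale the increase is visible.

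**Allowing for early termination.** Protocol 7.5 projects that 30% to 40% will stop treatment early. It does not say when, so assume those patients stay on drug for 25% to 75% of 26 weeks. Mean on-treatment time is 26 × (1 − d) + 26 × d × f, where d is the proportion stopping early and f the fraction of treatment they complete.

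- d = 0.4, f = 0.25: 15.6 + 2.6 = 18.2 weeks; ratio to 4 weeks 4.55
- d = 0.3, f = 0.75: 18.2 + 5.85 = 24.05 weeks; ratio 6.01

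The break-even then falls to roughly 4.6 to 6.0. This is approximate, because it uses mean exposure.

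**Follow-up 6, a separate check.** In the flow chart footnotes, "Each follow-up visit is to be scheduled from the EOT or early EOT visit". Follow-up 6 is planned at EOT +28 days with a +7 window. With the last dose one day before EOT, a completer's Follow-up 6 falls on Days 29 to 36 after the last dose, so the withdrawal period closes 1 to 8 days earlier.

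**The case against.** The strongest reply is that the plan has a placebo arm. Table 6.1: 2 applies the same periods to both arms, and SAP 7.8.1 summarises AEs by treatment. Iclepertin versus placebo within the same 28 days is unaffected by the 6.5-fold difference. This stands, and nothing suggests that the arms would be pooled. But the visible text neither lists that table nor makes it the main reading; the contrast Protocol 7.2.5 describes is between periods.

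Second, the section speaks of new AEs. An AE type never seen on treatment goes from zero to above zero and shows as an increase whatever the period lengths. This also stands. A reader might infer that any real withdrawal signal would look like a decrease, or that the analysis as a whole is biased towards reassurance. The documents do not support that: the problem is confined to the within-arm contrast, for AE types that also occur on treatment, below the break-even ratio.

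Third, SAP 7.8.1 refers to internal AE guidelines that are not available here. Its counting rule excludes counting events, not patient-based rates over time. An exposure-adjusted display under those guidelines cannot be ruled out, so the point concerns only what the visible text specifies.

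Finally, a reader might infer that Follow-up 6 data are lost, or that only 16 of the 28 days (28 − 12) are informative. Neither is a defect that produces the apparent decrease:

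- AEs are assigned by when they occur, so an onset on Days 1 to 28 that is reported at Follow-up 6 still counts. Later onsets leave this contrast but reach the follow-up AE table.
- Vital signs have their own Follow-up 6 window in SAP Table 6.7: 9, and the PWC-20 windows in Table 6.7: 10 run through Day 41 for that visit.
- Protocol 3.2 considers the 12-day elimination and judges 28 days sufficient. Days of falling drug level are not shown to be uninformative about withdrawal.

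**Conclusion.** The concern holds in limited form. Read as written, the within-arm contrast sets patient counts from 28 days against counts from up to 182 days with no stated adjustment. For AE types already present on treatment, a true rate increase below about 6.5-fold in completers would appear as a lower percentage off treatment. With the projected early termination, that threshold is about 4.6 to 6.0.

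The ratio of 6.5 follows from the documents. The percentages rest on an assumed constant hazard and on illustrative incidences and rate ratios; the lower thresholds rest on assumed discontinuation times. The analysis is descriptive, with no hypothesis test, and the comparison between arms within the withdrawal period remains sound. The Follow-up 6 misalignment of 1 to 8 days in completers is a minor, separate matter.

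**What to change.** In Protocol 7.2.5 and SAP 7.8.1:

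1. Report the contrast as patients with new-onset AEs per patient-time (for example, per 100 patient-weeks) in each period, or use the last 28 on-treatment days as an equal-length comparator.
2. State that iclepertin versus placebo within the 4-week withdrawal period is the main reading, and add that table to the SAP list.

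If the last 28 on-treatment days are used, show completers separately: in patients who stopped because of an AE, that window can contain the AE that led to stopping. If the internal AE guideline already requires exposure-adjusted rates, a sentence saying so for this contrast meets item 1.

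The cost is a few sentences and extra table columns. No new data are needed.
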